6.7. Study Early Discontinuation Criteria

The current clinical trial will be completed when the last participant finishes their final pre-specified study assessment or is otherwise permanently discontinued from the trial.

Early discontinuation of the study may occur at the discretion of the Sponsor in the event there is an unacceptable shift in the benefit-risk assessment of the investigational therapy (rimegepant) for the target population under investigation (adults living with migraine who are unsuitable for triptan use). The change in benefit-risk profile of the study drug may be derived from events (adverse events, serious adverse events, etc.) occurring within the

BHV3000-407 study and/or any other rimegepant safety data source, including other clinical trials, toxicological studies, or spontaneous reporting of real-world evidence.

7. STUDY DRUG MANAGEMENT

7.1. Description of Study Drug

7.1.1. Investigational Product

An investigational product, also known as investigational medicinal product in some regions, is defined as follows:

A pharmaceutical form of an active substance or placebo being tested or used as a reference in a clinical study, including products already with a marketing authorization but used or assembled (formulated or packaged) in a way different from the authorized form, or used for an unauthorized indication, or when used to gain further information about the authorized form.

The investigational product should be stored in a secure area according to local regulations. It is the responsibility of the Investigator to ensure that investigational product is only dispensed to study subjects. The investigational product must be dispensed only from official study sites by authorized personnel according to local regulations.

During the DBT Phase, investigational product/study drug/study medication is blinded rimegepant (BHV-3000) (PF-07899801) (75 mg ODT) and matching placebo, which will be provided by the Sponsor.

During the OLE Phase, investigational product/study drug/study medication is open label rimegepant (BHV-3000) (PF-07899801) (75 mg ODT), which will be provided by the Sponsor.

NOTE:

During the DBT or OLE Phase, if a dose of study drug for a given day is missed, lost, or otherwise unable to be taken, the subject should document that as a missed dose on the Study Drug Compliance Log and should NOT take another dose of study drug until the next scheduled dosing day, in accordance with the planned EOD dosing schedule.

Intervention Name	Rimegepant	Placebo
Type	drug	drug
Use	Experimental	Placebo
IMP or NIMP/AxMP	IMP	IMP
Dose Formulation	Orally disintegrating tablet (ODT)	Orally disintegrating tablet (ODT)

Unit Dose Strength(s)	75 mg	Placebo for 75 mg tablet
Dosage Level(s)	DBT phase: 75 mg	DBT phase : Placebo ODT
	OLE phase: 75 mg	OLE phase: not applicable
Route of Administration	Oral	Oral
Sourcing	Provided by the sponsor	Provided by the sponsor
Packaging and Labeling	Study intervention will be provided in multi-laminated blisters, sealed with a foil backing into wallet cards. Each blister wallet will be labeled as required per country requirement.	Study intervention will be provided in multi-laminated blisters, sealed with a foil backing into wallet cards. Each blister wallet will be labeled as required per country requirement.
SRSD	IB	Not applicable

7.1.2. Concomitant Therapy

In this protocol, concomitant therapy(ies) is/are standard of care for acute treatment and acute migraine medication for migraine treatment. The standard of care and acute migraine medications are not being provided by the Sponsor.

7.1.3. Packaging, Shipment and Storage

The product storage manager should ensure that the study drug is stored in accordance with the environmental conditions (temperature and light) as determined by the sponsor. Please see the Pharmacy Manual/Investigator Brochure for specific conditions. If concerns regarding the quality or appearance of the study drug arise, do not dispense the study drug and contact the sponsor/CRO immediately.

In the DBT Phase, subjects will receive blister cards containing 8 tablets of blinded rimegepant 75 mg ODT or matching placebo, heat-sealed into a wallet.

In the OLE Phase, subjects will receive blister cards containing 8 tablets of rimegepant 75 mg ODT, heat-sealed into a wallet.

7.2. Dose and Administration

During the DBT Phase, blinded rimegepant 75 mg ODT or matching placebo will be assigned to subjects at the Baseline Visit via the RTSM system. Subjects will be assigned enough IP at each visit to ensure appropriate supply between monthly (every 4 week) visits. Scheduled every other day (EOD) dosing with blinded study drug (regardless of migraine status) should be continued throughout the entire course of the DBT Phase. If the Week 12 Visit falls on a regularly scheduled dosing day, subjects should take their final dose of blinded study medication on that calendar day.

During the OLE Phase, wallets containing 8 tablets of open label rimegepant 75 mg ODT will be dispensed to subjects. Subjects will receive enough IP at the DBT Week 12 Visit, and

at the OLE Week 14 visit to ensure appropriate supply throughout the open label extension phase. Unscheduled visits to dispense study drug may be scheduled as needed. Scheduled every other day (EOD) dosing with open-label study drug (regardless of migraine status) should be continued throughout the entire course of the OLE Phase.

Day 1 of the OLE Phase is defined as Week 12 visit date plus 1 calendar day.

Dosing with open-label study drug (rimegepant 75 mg ODT) should BEGIN two calendar days after the final scheduled dosing day for blinded study drug, to maintain the EOD dosing schedule throughout the entire course of the trial (DBT and OLE Phases).

7.2.1. Method of Assigning Subject Identification

The Investigator or designee will need to access the Randomization and Trial Supply Management (RTSM) System in order to register each subject. Initially, after informed consent is obtained at the Screening Visit, the Investigator or designee will enter the subject into the study and obtain a subject number assignment.

Once a subject completes the study, or if a subject is discontinued early from the study, the Investigator or designee must access the RTSM to document discontinuation of the subject from participation in the study.

Immediately after written informed consent is obtained and before performing any study-related procedures, the site staff must obtain a subject identification by adding a new subject in the appropriate study-related system. In this study, an RTSM system will be utilized for obtaining subject identification and as the electronic data capture (EDC) system. Each subject will be assigned a unique 8-digit subject number through the appropriate study-related system. The subject number will consist of the 3-digit site number, a hyphen, and a unique 4-digit subject number. This subject number must not be reused for any other subject in the study. Subjects will maintain their subject number assigned at screening throughout the study.

At the Baseline Visit, eligible subjects will be randomized in a 1:1 ratio to blinded rimegepant (75 mg ODT) or matching placebo, dosed EOD. Randomization will be stratified by: 1) the number of migraine days reported to have occurred during the first 28-days of the Observation Phase (4-7 or 8-14); and 2) the number of recognized, orally-administered, preventive medication categories with previous inadequate response within 10 years of the Screening Visit (due to lack of efficacy, prior intolerance, or contraindication) (2 vs. 3-4 categories).

7.2.2. Selection and Timing of Dose and Administration

After confirming subject eligibility, registering a subject for randomization will trigger kit assignments at the Baseline visit; kit numbers will be obtained by the Investigator (or designee) via the RTSM system.

For the DBT Phase, study drug will be assigned via the RTSM system at Baseline and all subsequent DBT Phase dispensation visits. Subjects will be assigned 2 wallets containing 8

tablets of 75 mg ODT rimegepant or matching placebo at each dispensation visit to ensure appropriate supply between monthly (every 4 week) visits. The system will assign specific kit numbers for all study drug to be dispensed to the subject and there will be no dose adjustment allowed.

Once a kit has been assigned it cannot be dispensed to another study subject. Sites will be responsible for recording the kit numbers dispensed to the subject on the Drug Accountability Form provided in the Regulatory Binder, as well as ensure appropriate documentation of dispensation in the subject's medical record.

In the DBT Phase, study drug (rimegepant or matching placebo) will be assigned via the appropriate study-related system. There are no dose adjustments in this study and subjects will receive 8 tablets of study drug in a blister card heat-sealed into a wallet; subjects will be assigned more than 1 wallet at each visit to ensure appropriate supply between visits. Subjects will be dispensed study drug at the Baseline Visit, and the subjects will be instructed that they must take **one tablet EOD regardless of whether they have a migraine on that day**. This is the scheduled dosing regimen for the DBT Phase. Site staff should mark each wallet with the scheduled date of each dose to be taken when dispensing the study drug.

In the DBT Phase, subjects will be instructed that they must take **one tablet EOD regardless of whether they have a migraine on that day**. Dosing should occur around the same time for each scheduled EOD dose. It is preferred that subjects' dose in the morning; however, it is more important that the subject consistently dose at approximately the same time for each scheduled EOD dose. The time of dosing should be consistent throughout the study. If the subject has a migraine on a day when they **already took study drug**, then the subject can take permitted acute migraine medication (see Section 16.4 Appendix 4), as needed, and in accordance with the standard of care.

During the DBT Phase, if a dose of study drug for a given day is missed, lost, or otherwise unable to be taken, the subject should document that as a missed dose on the Study Drug Compliance Log and should NOT take another dose of study drug until the next scheduled dosing day, in accordance with the planned EOD dosing schedule.

Scheduled every other day (EOD) dosing with blinded study drug (regardless of migraine status) should be continued throughout the entire course of the DBT Phase. If the Week 12 Visit falls on a regularly scheduled dosing day, subjects should take their final dose of blinded study medication on that calendar day.

During the OLE Phase, open label rimegepant 75 mg ODT will be assigned via the RTSM system at the DBT EOT visit and at the Week 14 Visit. Subjects will be instructed that they must take one tablet every other calendar day, regardless of whether they have a migraine on that day or not. If the subject has a migraine on a day when they **already took open-label drug**, then the subject can take permitted acute migraine medication (see Section 16.4 Appendix 4), as needed, and in accordance with the standard of care.

Scheduled every other day (EOD) dosing with open-label study drug (regardless of migraine status) should be continued throughout the entire course of the OLE Phase.

Day 1 of the OLE Phase is defined as Week 12 visit date plus 1 calendar day.

Dosing with open-label study drug (rimegepant 75 mg ODT) should BEGIN two calendar days after the final scheduled dosing day for blinded study drug, to maintain the EOD dosing schedule throughout the entire course of the trial (DBT and OLE Phase. In both the DBT and OLE Phases, subjects must be instructed that they CANNOT take more than one tablet of study drug/open label drug every other day (EOD) during the study, in accordance with the protocol.

7.2.3. Dose Modifications

There will be no dose adjustments in this study.

7.2.4. Dose Interruptions

If a subject experiences an AE that requires interruption in study drug, the Investigator should consult with the Sponsor medical monitor to evaluate the need for any additional tests prior to re-starting study drug.

7.3. Blinding and Unblinding

Blinding is critical to the integrity of this clinical study. However, in the event of a medical emergency or pregnancy in an individual subject, in which knowledge of the investigational product is critical to the subject's management, the blind for that subject may be broken by the treating physician.

The BHV3000-407 (C4951012) study is a double-blind placebo-controlled trial being conducted in accordance with Good Clinical Practice (GCP), International Conference on Harmonization (ICH) guidelines, Ethics Committee (EC) requirements, and all applicable regulations. Within the BHV3000-407 (C4951012) study, blinding and randomization are utilized to minimize the influence of bias on the conduct of the trial and its associated outcomes.

At the Baseline Visit, eligible subjects will be randomized 1:1 across two blinded treatment arms (blinded rimegepant 75 mg or matching placebo) for the duration of the Double-Blind Treatment (DBT) Phase. Blinded study drug assignment will be issued by centralized Interactive Response Technology (IRT) to follow block randomization of an undisclosed length. Randomization will be stratified by: 1) the number of migraine days reported to have occurred during the first 28-days of the Observation Phase (4-7 or 8-14) and 2) the number of recognized, orally-administered, preventive medication categories with previous inadequate response within 10 years of the Screening Visit (due to lack of efficacy, prior intolerance, or contraindication) (2 vs. 3-4 categories) (see Section 7.2.1).

BHV3000-407 (C4951012) is a double-blind study in which neither the subject nor the Site staff involved in the conduct of the study or clinical evaluation of subjects are aware of study drug assignment. Sponsor staff too will be blinded to subjects' treatment assignment, except for those sponsor staff involved in the assignment or distribution of blinded study drug.

Blinded treatments (double-blind rimegepant or matching placebo) are packaged and labeled in accordance with the kit list, and supplies are dispensed through the IRT per the randomization schedule. Blinded rimegepant and blinded placebo are both oral disintegrating tablets matched in appearance, texture, and taste, and are supplied to the trial center in a manner that ensures no one involved in the conduct of the trial is aware of the specific treatment allocated to any particular subject.

Unblinding (breaking the blind for a single subject) should be considered only when knowledge of the treatment assignment is deemed by the Investigator, as essential for the proper care of the subject. The IRT will be programmed with blind-breaking instructions. In case of an emergency, the Investigator has the sole responsibility for determining if unblinding of a subject's treatment assignment is warranted. Subject safety must always be the first consideration in making such a determination. If the Investigator decides that unblinding is warranted, the Investigator should make every effort to contact the study Medical Monitor prior to unblinding a subject's treatment assignment unless this could delay further management of the subject. If a subject's treatment assignment is unblinded, the Sponsor must be notified within 24 hours after breaking the blind. The date and reason that the blind was broken must be recorded in the source documentation and CRF.

In cases of accidental unblinding, the Site should contact the Medical Monitor and ensure every attempt is made to preserve the blind for remaining site personnel.

Sponsor staff will be unblinded after the last subject completes the Double-blind Treatment End of Treatment Visit or, in the event the last subject has discontinued early from the study, completes the Week 12 OLE / End of Treatment Visit, or is otherwise discontinued from the trial (e.g., lost to follow-up) (see protocol Section 6.6). Once the overall study is complete (i.e., after the last subject completes the Follow-up Week 2 Visit or is otherwise discontinued from the study), individual subject assignments will be made available to associated Investigators, upon request.

In the event of a Quality Assurance audit, the auditor(s) will be allowed access to unblinded study intervention records at the site(s) to verify that randomization/dispensing has been done accurately.

7.4. Treatment Compliance

Responsible study personnel will dispense the study drug. Subjects are required to finish a wallet of study drug before starting a new wallet. Accountability and compliance verification should be documented in the subject's study records.

Subjects must be counseled on the importance of taking the study drug as directed (see Section 7.2.2). Treatment compliance and review of study drug doses through review of returned study drug should be assessed by site staff at each study visit. Discrepancies between review of study drug and information provided by subject must be documented in the source record. Investigators should inform subjects that involuntary termination from the study will occur in cases where non-compliance is identified. Study staff should contact a subject between the monthly study visits if the subject demonstrates non-compliance with the

eDiary and document the contact in the source, to identify potential lost to follow-up subjects as early as possible.

Investigators must monitor subjects for possible cases of abuse of study drug (subjects taking study drug for non-therapeutic purposes, e.g., for psychoactive effects such as high or euphoria). Investigators should also assess study drug accountability discrepancies (e.g., missing study drug, loss of medication, or non-compliance cases in which more study drug was used, as compared to expected). Investigators should obtain more information and explanation from subjects when there are study drug accountability discrepancies (see Section 8.1.1).

Cases of study drug non-adherence, including subjects who discontinue treatment without returning study drug, should be reported as protocol deviations.

All cases of treatment non-compliance, during the DBT Phase, are to be discussed with the Sponsor, and corrective training is to be completed and documented, prior to the subjects enrollments into the OLE Phase.

Cases of excess dosing (e.g., taking >1 tablet of study drug every other day) should be reported as protocol deviations. In the event that an occurrence(s) of excess dosing is believed, in the opinion of the Principal Investigator, to have possibly caused or exacerbated a clinically-significant adverse outcome or serious adverse outcome, the AE resulting from the excess dosing should be reported as aSAE.

Dosing errors not associated with a SAE (e.g., accidentally taking 2 tablets EOD) need only be reported as deviations.

Compliance with study intervention will be defined as:

- $\geq 80\%$ (and ideally, up to 100%) of study-supplied intervention from Day 1 through the Treatment Phase are expected to be consumed.
- Post randomization, at each dispensation visit (refer to Table 1), subjects who are <80% compliant must be re-educated on the importance of EOD self administration of study intervention.
- Overall aim: maintain $\geq 80\%$ compliance over the duration of dosing with randomized study intervention.

7.5. Destruction and Return of Study Drug

All unused and/or partially used study drug can be sent back to the determined destruction facility only after being inspected and reconciled by the responsible Study monitor or the Sponsor's designee. If it is site policy to destroy study drug on site, it is the Investigator's responsibility to ensure that arrangements have been made for the disposal, procedures for proper disposal have been established according to the applicable regulations, guidelines and institutional procedures, and appropriate records of the disposal have been documented. The

unused study drugs can only be destroyed after being inspected and reconciled by the responsible Study Monitor or the Sponsor's designee.

8. ADVERSE EVENTS

An Adverse Event (AE) is defined as any new untoward medical occurrence or worsening of a pre-existing medical condition in a subject or clinical investigation subject administered an investigational (medicinal) product and that does not necessarily have a causal relationship with this treatment. An AE can therefore be any unfavorable and unintended sign (including an abnormal laboratory finding for example) or symptom, or disease temporally associated with the use of the investigational product, whether or not considered related to the investigational product.

Adverse events can be spontaneously reported or elicited during an open-ended questioning, examination, or evaluation of a subject. In order to prevent reporting bias, subjects should not be questioned regarding the specific occurrence of one or more AEs. Adverse events should be reported after the first dose of study drug.

If a specific diagnosis or syndrome is identified by the Investigator, this should be recorded as the AE, rather than recording (as separate AEs) the individual signs/symptoms or clinically significant laboratory abnormalities known to be associated with and considered by the Investigator to be a component of, the disease/syndrome.

Definition of terms related to all Adverse Events (serious and non-serious):

Mild: Is usually transient and may require only minimal treatment or therapeutic intervention. The event does not generally interfere with usual activities of daily living.

Moderate: Is usually alleviated with additional specific therapeutic intervention. The event interferes with usual activities of daily living, causing discomfort but poses no significant or permanent risk of harm to the subject.

Severe: Interrupts usual activities of daily living, significantly affects clinical status, or may require intensive therapeutic intervention.

Life threatening: An AE is life threatening if the subject was at immediate risk of death from the event as it occurred, i.e., it does not include a reaction that if it had occurred in a more serious form might have caused death. For example, drug induced hepatitis that resolved without evidence of hepatic failure would not be considered life threatening even though drug induced hepatitis can be fatal.

Hospitalization: AEs requiring hospitalization should be considered SAEs. Hospitalization for elective surgery or routine clinical procedures that are not the result of AE (e.g., elective surgery for a pre-existing condition that has not worsened) need not be considered AEs or SAEs. If anything untoward is reported during the procedure, that occurrence must be reported as an AE, either 'serious' or 'non-serious' according to the usual criteria.

Assessment for Determining Relationship of AE to Study Drug:

The relatedness of each AE to study drug must be classified based on medical judgement and according to the following categories. The definitions are as follows:

Related: This category applies to AEs that are considered, with a high degree of certainty, to be related to the study drug. An AE may be considered related when it follows a temporal sequence from the administration of study drug, it cannot reasonably be explained by the known characteristics of the subject's clinical state, environment, or toxic factors, or other modes of therapy administered to the subject. An AE may be considered related when it follows a known pattern of response to the study drug, or if the AE reappears upon re-challenge.

Possibly related (non-serious AEs only): This category applies to AEs that are considered to have a possible connection to study drug and relationship cannot be ruled out with certainty.

Unlikely related (non-serious AEs only): This category applies to AEs that do not follow a reasonable temporal sequence from the administration of the study drug. The AE may readily have been produced by the subject's clinical state, environmental or toxic factors, or other modes of therapy administered to the subject.

Unrelated: This category applies to AEs that are considered with a high degree of certainty to be due only to extraneous causes (e.g., subject's clinical state, environment, toxic factors, disease under study, etc.) and does not meet the criteria of other categories above.

There are two types of adverse events, Serious Adverse Events (SAE) and Non-Serious Adverse Events (AEs).

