8.1.2. Collection and Reporting Serious Adverse Events

Following the subject's written consent to participate in the study, all SAEs, whether related or not related to study drug, must be collected, including those thought to be associated with protocol-specific procedures. All SAEs must be collected from signing of consent through the 2-week Follow-up Visit. Unresolved SAEs at the time of the 2-week Follow-up Visit should be monitored until resolution of the acute aspects of the safety event, per the opinion of the Investigator. The Investigator should report any SAE occurring beyond the 2-week Follow-up Visit when the event is believed to be related to study drug or other protocol-specific procedures.

All SAEs should be followed to resolution or stabilization.

An SAE report should be completed for any event where doubt exists regarding its status of seriousness.

If the Investigator believes that an SAE is not related to the study drug but is potentially related to the conditions of the study (such as a withdrawal of previous therapy or a complication related to study procedure), the relationship should be specified in the narrative section of the SAE Report.

SAEs, whether related or not related to study drug, overdose (see Section 8.3), potential drug induced liver injury, (see Section 8.4) and pregnancies (see Section 8.5.1) must be reported within 24 hours of the Investigator becoming aware of the event. The Investigator is responsible for submitting all applicable events to the Independent Review Board (IRB) as per the IRB's reporting requirements. Additionally, the Investigator, or designated staff, is responsible for entering the SAE information into the Case Report Form (CRF) and/or system (i.e., event term, start/stop dates, causality, and severity).

Any serious adverse event must be reported immediately or no later than 24 hours after awareness of the event to Pfizer Drug Safety Unit (DSU) either via the Pfizer SAE Submission Assistant (PSSA) tool or using the Pfizer CT SAE report form that must be sent by facsimile (fax) to your country's Pfizer DSU. The CT SAE Report Form should only be used as a backup in the event PSSA is not operational.

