If only limited information is initially available, follow-up reports are required. If an ongoing SAE changes in its intensity or relationship to study drug, or if new information becomes available, a follow-up SAE report should be sent within 24 hours of the Investigator becoming aware of the updated information using the same procedure used for the transmission of the initial SAE and the same event term should be used.

The minimum information required for an initial SAE report is:

- Sender of report (Site number, Investigator name)
- Subject identification (subject number)

- Protocol number
- SAE term (if an SAE is being reported)

The Sponsor or specified designee/authorized representative will report suspected unexpected serious adverse reactions (SUSARs) in an expedited manner (without delay) to the Regulatory Authorities and Ethics Committees concerned, in accordance with Food and Drug Administration Code of Federal Regulations (CFR) 21 CFR Parts 312 and 320, Clinical Trials Regulation No 536/2014, and the Detailed Guidance on collection, verification and presentation of adverse reaction reports arising from clinical trials on IPs for human use (ENTR/CT3) and also in accordance with country-specific requirements.

The Sponsor or specified designee/authorized representative shall notify the Investigator of the following information:

Any AE that is both serious and unexpected and is suspected of being related to the use of the IP in this study or in other studies (i.e., SUSAR).

Where required by local legislation, the Investigator shall notify his/her IRB/EC promptly of these new serious and unexpected AE(s) or significant risks to subjects.

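### For SAEs the protocol's causality scale has only 'Related' and 'Unrelated', both requiring high certainty, so an SAE with a plausible but uncertain link has no category and no default rule

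*Protocol*

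**What the plan says.** Protocol section 8, under the assessment of relationship to study drug, makes classification compulsory: "The relatedness of each AE to study drug must be classified based on medical judgement and according to the following categories". Four categories follow.

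- Related: "This category applies to AEs that are considered, with a high degree of certainty, to be related to the study drug". Further sentences soften this: "An AE may be considered related when it follows a known pattern of response to the study drug, or if the AE reappears upon re-challenge", and likewise where timing fits and nothing else reasonably explains the event.
- Possibly related: "Possibly related (non-serious AEs only): This category applies to AEs that are considered to have a possible connection to study drug".
- Unlikely related: "Unlikely related (non-serious AEs only): This category applies to AEs that do not follow a reasonable temporal sequence".
- Unrelated: "Unrelated: This category applies to AEs that are considered with a high degree of certainty to be due only to extraneous causes". The event must also fail the criteria of the other categories.

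On reporting, section 8.1.2 says that "all SAEs, whether related or not related to study drug, must be collected", requires any SAE to go to the sponsor's safety unit within 24 hours, and has the site enter causality with the SAE information. The sponsor or its designee makes the SUSAR reports. Its notice to investigators covers "Any AE that is both serious and unexpected and is suspected of being related to the use of the IP in this study". SAEs after the 2-week Follow-up Visit are to be reported when the investigator believes them related to study drug or to protocol procedures.

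Section 8.5.1 has infant deaths after one month reported as SAEs when the investigator judges them related, or possibly related, to exposure.

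Protocol section 9.3.2 takes causality in the tables from the investigator. SAP section 6.4.1.2 has an overview row for SAEs related to study drug. SAP section 6.4.1 refers to the Core SAP for the definition of related AEs, and that document is not available here.

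**The concern.** The two middle categories carry the judgement that is most common when causality is assessed: a link that can be neither asserted nor excluded. The protocol offers that judgement for non-serious events and withdraws it for serious ones. Two events with the same causal evidence can then be recorded differently only because one of them was serious.

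At stake are the meaning of the related-SAE row, the comparability of serious and non-serious events in the tables of related AEs (SAP sections 6.4.1.3 and 6.4.1.4), and a clear rule for reporting SAEs that arise after follow-up ends.

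**Working it through.** The documents give no figure to reproduce, so the check is a reading of the text.

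**Step 1. Which categories can an SAE take?**

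| Category (Protocol section 8) | Open to SAEs? | Standard |
|---|---|---|
| Related | Yes | High certainty that the drug is involved |
| Possibly related | No | Possible connection that cannot be ruled out |
| Unlikely related | No | No reasonable temporal sequence |
| Unrelated | Yes | High certainty of extraneous causes only, and no other category met |

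**Step 2. Does an uncertain SAE fit either open category?** Take an SAE with compatible timing and a competing explanation. It fails the high-certainty standard of 'Related'. The permissive sentences do not rescue it: one needs the absence of another reasonable explanation, and the others need a known response pattern or re-challenge. It also fails 'Unrelated', because the causes are not known with high certainty to be extraneous only. No tie-break is stated.

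**Step 3. Will such SAEs arise?** The protocol produces them by rule. Section 8.4 requires potential Hy's law cases to be reported as SAEs before the work-up of cause is complete. Section 8.2.1 has a non-serious AE reported as an SAE if it becomes serious, so an event recorded as possibly related would lose its category with no change in the evidence.

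**Step 4. Do other sections use the same standard?** No. Section 8.1.2 uses suspicion for serious unexpected events and the investigator's belief for SAEs after follow-up. Section 8.5.1 uses a possible relationship for a serious event. None of these matches the standard in section 8.

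**Step 5. How far can the table move?** Let R be the SAEs that clearly meet 'Related', and U those of uncertain causality. The related-SAE count lies between R (all uncertain cases called unrelated) and R + U (all called related). The documents give neither R nor U.

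For scale only, assume that 1% to 2% of about 600 randomized subjects have an SAE in the double-blind phase. That is 600 × 0.01 = 6 to 600 × 0.02 = 12 subjects. One reclassified subject is then 1/12 (8%) to 1/6 (17%) of all subjects with an SAE. The 1% to 2% is an assumption, and the open-label phase would add an unknown number.

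**The case against.** The strongest reply is that nothing important depends on the category. Through the 2-week Follow-up Visit every SAE reaches the sponsor within 24 hours whether or not it is thought related. The sponsor makes the SUSAR reports on a standard of suspicion, and nothing binds it to the investigator's category. SAEs are a secondary endpoint regardless of causality. They are tabulated and listed without a causality filter, and those on rimegepant or in follow-up are marked for narratives (SAP sections 6.4.1 and 6.4.6). The related-SAE row is one descriptive line. A two-level scale for SAEs is also a reasonable design in itself.

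Most of this stands, and it rules out a stronger reading that a reader might infer: that related-SAE counts and expedited reports will be too low. The documents do not support that. 'Unrelated' needs high certainty too, so the text does not push doubtful cases there, and the permissive wording under 'Related' could draw some of them in. The count could be raised or lowered.

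The reply does not remove the gap. A two-level scale works only if the two levels cover every case, and these do not. The missing Core SAP and SAE form guidance might pool possibly related with related, but pooling cannot recover a judgement that was never collected for SAEs.

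**Conclusion.** The point holds as a defect in a stated rule. An SAE of uncertain causality has no valid category and no default, and sections 8, 8.1.2 and 8.5.1 apply different standards.

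Three consequences follow. The investigator-assessed related-SAE row is ambiguous by up to U events; it may be too low, but its direction cannot be derived. Serious and non-serious events with the same evidence may be classified differently. Reporting of SAEs after the 2-week Follow-up Visit is unclear, because there relatedness decides whether the event is reported at all.

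Suppression of SUSAR reports is not shown. The efficacy analyses and the overall SAE counts are unaffected. The conclusion assumes that the SAE form follows section 8. If its causality question is already worded on reasonable possibility, what remains is an inconsistency in the protocol text.

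**What to change.** For SAEs, define 'Related' as a reasonable possibility that study drug caused the event, stating that this covers possibly related, and 'Unrelated' as no reasonable possibility. Reconcile Protocol section 8 with sections 8.1.2 (both the suspicion wording and the rule for SAEs after follow-up) and 8.5.1. Check that the SAE form guidance and the Core SAP definition of related AEs match.

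The cost is protocol and CRF-guideline wording and a letter to sites. Sample size, design and efficacy analyses do not change. The downside is that a few more SAEs may be recorded as related.
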